**Table 27 – Biochemistry – Safety population**

	Total (n=xx)				
	Screening	Baseline	Visit xx	End of study treatment	End of study
Urea, n (%)					
Normal					
Abnormal, clinically irrelevant					
Abnormal, clinically relevant					
Total					
Baseline versus current visit					
Normal - Normal	-	-	-	-	-
Normal - Abnormal, clinically irrelevant	-	-	-	-	-
Normal - Abnormal, clinically relevant	-	-	-	-	-
Abnormal, clinically irrelevant - Normal	-	-	-	-	-
Abnormal, clinically irrelevant - Abnormal, clinically irrelevant	-	-	-	-	-
Abnormal, clinically irrelevant - Abnormal, clinically relevant	-	-	-	-	-
Abnormal, clinically relevant - Normal	-	-	-	-	-
Abnormal, clinically relevant - Abnormal, clinically relevant	-	-	-	-	-
Abnormal, clinically relevant - Abnormal, clinically irrelevant	-	-	-	-	-
Glucose, n (%)					
Normal					
Abnormal, clinically irrelevant					
Abnormal, clinically relevant					
Total					
Baseline versus current visit					
Normal - Normal	-	-	-	-	-
Normal - Abnormal, clinically irrelevant	-	-	-	-	-
Normal - Abnormal, clinically relevant	-	-	-	-	-
Abnormal, clinically irrelevant - Normal	-	-	-	-	-
Abnormal, clinically irrelevant - Abnormal, clinically irrelevant	-	-	-	-	-
Abnormal, clinically irrelevant - Abnormal, clinically relevant	-	-	-	-	-
Abnormal, clinically relevant - Normal	-	-	-	-	-
Abnormal, clinically relevant - Abnormal, clinically relevant	-	-	-	-	-
Abnormal, clinically relevant - Abnormal, clinically irrelevant	-	-	-	-	-

**Table 27 (Cont.) – Biochemistry – Safety population**

	Total (n=xx)				
	Screening	Baseline	Visit xx	End of study treatment	End of study
AST, n (%)					
Normal					
Abnormal, clinically irrelevant					
Abnormal, clinically relevant					
Total					
Baseline versus current visit					
Normal - Normal	-	-	-	-	-
Normal - Abnormal, clinically irrelevant	-	-	-	-	-
Normal - Abnormal, clinically relevant	-	-	-	-	-
Abnormal, clinically irrelevant - Normal	-	-	-	-	-
Abnormal, clinically irrelevant - Abnormal, clinically irrelevant	-	-	-	-	-
Abnormal, clinically irrelevant - Abnormal, clinically relevant	-	-	-	-	-
Abnormal, clinically relevant - Normal	-	-	-	-	-
Abnormal, clinically relevant - Abnormal, clinically relevant	-	-	-	-	-
Abnormal, clinically relevant - Abnormal, clinically irrelevant	-	-	-	-	-
ALT, n (%)					
Normal					
Abnormal, clinically irrelevant					
Abnormal, clinically relevant					
Total					
Baseline versus current visit					
Normal - Normal	-	-	-	-	-
Normal - Abnormal, clinically irrelevant	-	-	-	-	-
Normal - Abnormal, clinically relevant	-	-	-	-	-
Abnormal, clinically irrelevant - Normal	-	-	-	-	-
Abnormal, clinically irrelevant - Abnormal, clinically irrelevant	-	-	-	-	-
Abnormal, clinically irrelevant - Abnormal, clinically relevant	-	-	-	-	-
Abnormal, clinically relevant - Normal	-	-	-	-	-
Abnormal, clinically relevant - Abnormal, clinically relevant	-	-	-	-	-
Abnormal, clinically relevant - Abnormal, clinically irrelevant	-	-	-	-	-

**Table 27 (Cont.) – Biochemistry – Safety population**

	Total (n=xx)				
	Screening	Baseline	Visit xx	End of study treatment	End of study
Creatinine clearance, n (%)					
Normal					
Abnormal, clinically irrelevant					
Abnormal, clinically relevant					
Total					
Baseline versus current visit					
Normal - Normal	-	-	-	-	-
Normal - Abnormal, clinically irrelevant	-	-	-	-	-
Normal - Abnormal, clinically relevant	-	-	-	-	-
Abnormal, clinically irrelevant - Normal	-	-	-	-	-
Abnormal, clinically irrelevant - Abnormal, clinically irrelevant	-	-	-	-	-
Abnormal, clinically irrelevant - Abnormal, clinically relevant	-	-	-	-	-
Abnormal, clinically relevant - Normal	-	-	-	-	-
Abnormal, clinically relevant - Abnormal, clinically relevant	-	-	-	-	-
Abnormal, clinically relevant - Abnormal, clinically irrelevant	-	-	-	-	-
Serum creatinine, n (%)					
Normal					
Abnormal, clinically irrelevant					
Abnormal, clinically relevant					
Total					
Baseline versus current visit					
Normal - Normal	-	-	-	-	-
Normal - Abnormal, clinically irrelevant	-	-	-	-	-
Normal - Abnormal, clinically relevant	-	-	-	-	-
Abnormal, clinically irrelevant - Normal	-	-	-	-	-
Abnormal, clinically irrelevant - Abnormal, clinically irrelevant	-	-	-	-	-
Abnormal, clinically irrelevant - Abnormal, clinically relevant	-	-	-	-	-
Abnormal, clinically relevant - Normal	-	-	-	-	-
Abnormal, clinically relevant - Abnormal, clinically relevant	-	-	-	-	-
Abnormal, clinically relevant - Abnormal, clinically irrelevant	-	-	-	-	-

**Table 27 (Cont.) – Biochemistry – Safety population**

	Total (n=xx)				
	Screening	Baseline	Visit xx	End of study treatment	End of study
Calcium, n (%)					
Normal					
Abnormal, clinically irrelevant					
Abnormal, clinically relevant					
Total					
Baseline versus current visit					
Normal - Normal	-	-	-	-	-
Normal - Abnormal, clinically irrelevant	-	-	-	-	-
Normal - Abnormal, clinically relevant	-	-	-	-	-
Abnormal, clinically irrelevant - Normal	-	-	-	-	-
Abnormal, clinically irrelevant - Abnormal, clinically irrelevant	-	-	-	-	-
Abnormal, clinically irrelevant - Abnormal, clinically relevant	-	-	-	-	-
Abnormal, clinically relevant - Normal	-	-	-	-	-
Abnormal, clinically relevant - Abnormal, clinically relevant	-	-	-	-	-
Abnormal, clinically relevant - Abnormal, clinically irrelevant	-	-	-	-	-
Sodium, n (%)					
Normal					
Abnormal, clinically irrelevant					
Abnormal, clinically relevant					
Total					
Baseline versus current visit					
Normal - Normal	-	-	-	-	-
Normal - Abnormal, clinically irrelevant	-	-	-	-	-
Normal - Abnormal, clinically relevant	-	-	-	-	-
Abnormal, clinically irrelevant - Normal	-	-	-	-	-
Abnormal, clinically irrelevant - Abnormal, clinically irrelevant	-	-	-	-	-
Abnormal, clinically irrelevant - Abnormal, clinically relevant	-	-	-	-	-
Abnormal, clinically relevant - Normal	-	-	-	-	-
Abnormal, clinically relevant - Abnormal, clinically relevant	-	-	-	-	-
Abnormal, clinically relevant - Abnormal, clinically irrelevant	-	-	-	-	-

**Table 27 (Cont.) – Biochemistry – Safety population**

	Total (n=xx)				
	Screening	Baseline	Visit xx	End of study treatment	End of study
Potassium, n (%)					
Normal					
Abnormal, clinically irrelevant					
Abnormal, clinically relevant					
Total					
Baseline versus current visit					
Normal - Normal	-	-	-	-	-
Normal - Abnormal, clinically irrelevant	-	-	-	-	-
Normal - Abnormal, clinically relevant	-	-	-	-	-
Abnormal, clinically irrelevant - Normal	-	-	-	-	-
Abnormal, clinically irrelevant - Abnormal, clinically irrelevant	-	-	-	-	-
Abnormal, clinically irrelevant - Abnormal, clinically relevant	-	-	-	-	-
Abnormal, clinically relevant - Normal	-	-	-	-	-
Abnormal, clinically relevant - Abnormal, clinically relevant	-	-	-	-	-
Abnormal, clinically relevant - Abnormal, clinically irrelevant	-	-	-	-	-
Chloride, n (%)					
Normal					
Abnormal, clinically irrelevant					
Abnormal, clinically relevant					
Total					
Baseline versus current visit					
Normal - Normal	-	-	-	-	-
Normal - Abnormal, clinically irrelevant	-	-	-	-	-
Normal - Abnormal, clinically relevant	-	-	-	-	-
Abnormal, clinically irrelevant - Normal	-	-	-	-	-
Abnormal, clinically irrelevant - Abnormal, clinically irrelevant	-	-	-	-	-
Abnormal, clinically irrelevant - Abnormal, clinically relevant	-	-	-	-	-
Abnormal, clinically relevant - Normal	-	-	-	-	-
Abnormal, clinically relevant - Abnormal, clinically relevant	-	-	-	-	-
Abnormal, clinically relevant - Abnormal, clinically irrelevant	-	-	-	-	-

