5.4 Laboratory Assessments

Normal ranges for the study laboratory parameters must be supplied to Roche before the study starts.

Efficacy Laboratory Assessments

Laboratory parameters will not be considered for the purpose of efficacy assessment.

Safety Laboratory Assessments

All safety laboratory assessments will be performed at local laboratories.

The following will be completed according to the Schedule of Assessments:

Blood tests with counts of the three series (leukocytes with neutrophils, haemoglobin, and platelets). This information will be obtained in the 21 days before initiation of treatment.

Biochemistry: LDH, alkaline phosphatase, ASAT, ALAT, total bilirubin, serum creatinine, creatinine clearance (if indicated), calcium, electrolytes, glucose and urea. This information will be obtained in the 21 days before initiation of treatment.

Prothrombin time, INR and aPTT. This information will be obtained in the 7 days before initiation of treatment.

Pregnancy test (urine or blood) in women of childbearing age, to be performed at screening and in the 1st day of study treatment (baseline), before the intake of study medication and at the end of study treatment.

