Diarrhoea has occurred in patients on erlotinib, and moderate or severe diarrhoea should be treated with loperamide. In some cases, dose reduction may be necessary. In the event of severe or persistent diarrhoea, nausea, anorexia, or vomiting associated with dehydration, erlotinib therapy should be interrupted and appropriate measures should be taken to treat the dehydration. There have been rare reports of hypokalaemia and renal failure (including fatalities). Some reports of renal failure were secondary to severe dehydration due to diarrhoea, vomiting and/or anorexia while others were confounded by concomitant chemotherapy. In more severe or persistent cases of diarrhoea, or cases leading to dehydration, particularly in groups of patients with aggravating risk factors (concomitant medications, symptoms or diseases or other predisposing conditions including advanced age), erlotinib therapy should be interrupted and appropriate measures should be taken to intensively rehydrate the patients intravenously. In addition, renal function and serum electrolytes including potassium should be monitored in patients at risk of dehydration.

Hepatitis, Hepatic Failure

Rare cases of hepatic failure (including fatalities) have been reported during use of erlotinib. Confounding factors have included pre-existing liver disease or concomitant hepatotoxic medications. Therefore, in such patients, periodic liver function testing should be considered. Erlotinib dosing should be interrupted if changes in liver function are severe.

Gastrointestinal perforation

Patients receiving erlotinib are at increased risk of developing gastrointestinal perforation, which was observed uncommonly (including some cases with a fatal outcome). Patients receiving concomitant anti-angiogenic agents, corticosteroids, non-steroidal anti-inflammatory drugs (NSAIDs), and/or taxane based chemotherapy, or who have prior history of peptic ulceration or diverticular disease are at increased risk. Erlotinib should be permanently discontinued in patients who develop gastrointestinal perforation).

Bullous and exfoliative skin disorders

Bullous, blistering and exfoliative skin conditions have been reported, including very rare cases suggestive of Stevens-Johnson syndrome/toxic epidermal necrolysis, which in some cases were fatal. Erlotinib treatment should be interrupted or discontinued if the patient develops severe bullous, blistering or exfoliating conditions.

Ocular Disorders

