8.2.4 Safety Data Analysis

The safety analysis population will include all subjects who receive at least one dose and had a safety assessment performed at baseline. All safety parameters will be summarized using descriptive measures and presented in tables based on this safety population.

Adverse event data will be presented in frequency tables (overall and by intensity) by body system. In tables showing the overall incidence of adverse events, subjects who experienced the same event on more than one occasion are counted only once in the calculation of the event frequency.

For selected events of particular interest summary tables will be presented for time to first onset of the event and for the total number of episodes. Every occurrence of an event in any subject will be counted in the total number of episodes but successive reports of an identical event in the same phase (treatment, follow-up) will be combined (concatenated) into a one episode if the end date of the earlier event was the same as the start date of the later event, or if the end date of the earlier event was missing.

All AEs and laboratory variables will be assessed according to the NCI CTC-AE version 4.0 grading system.

Laboratory values will be listed with flagging of values outside of normal range, and summarized in shift from baseline tables.

Information on the study drug will be summarized by duration, starting dose, dose per day and cumulative dose using descriptive statistics.

All AEs and laboratory variables will be assessed according to the NCI CTC-AE version 4.0 grading system.

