### **5.3.10.4 Laboratory data**

Laboratory assessment will be carried out at the screening visit and all visits during the treatment period. For the following laboratory parameters:

- 1) Hematology (hemoglobin, leucocytes, neutrophils, platelets),
- 2) Coagulation (prothrombin time, activated partial thromboplastin (aPTT), international normalized ratio (INR – only at the screening visit) and
- 3) Biochemistry (urea, glucose, AST, ALT, creatinine clearance (if indicated), serum creatinine, calcium, sodium, potassium, chloride, LDH, alkaline phosphatase, total bilirubin)

the percentage of patients with abnormal clinically relevant values will be assessed.

Laboratory will be summarized in shift from baseline tables.

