**Table 25 – Hematology – Safety population**

	Total (n=xx)				
	Screening	Baseline	Visit xx	End of study treatment	End of study
Hemoglobin, n (%)					
Normal					
Abnormal, clinically irrelevant					
Abnormal, clinically relevant					
Total					
Baseline versus current visit					
Normal - Normal	-	-	-	-	-
Normal - Abnormal, clinically irrelevant	-	-	-	-	-
Normal - Abnormal, clinically relevant	-	-	-	-	-
Abnormal, clinically irrelevant - Normal	-	-	-	-	-
Abnormal, clinically irrelevant - Abnormal, clinically irrelevant	-	-	-	-	-
Abnormal, clinically irrelevant - Abnormal, clinically relevant	-	-	-	-	-
Abnormal, clinically relevant - Normal	-	-	-	-	-
Abnormal, clinically relevant - Abnormal, clinically relevant	-	-	-	-	-
Abnormal, clinically relevant - Abnormal, clinically irrelevant	-	-	-	-	-
Leucocytes, n (%)					
Normal					
Abnormal, clinically irrelevant					
Abnormal, clinically relevant					
Total					
Baseline versus current visit					
Normal - Normal	-	-	-	-	-
Normal - Abnormal, clinically irrelevant	-	-	-	-	-
Normal - Abnormal, clinically relevant	-	-	-	-	-
Abnormal, clinically irrelevant - Normal	-	-	-	-	-
Abnormal, clinically irrelevant - Abnormal, clinically irrelevant	-	-	-	-	-
Abnormal, clinically irrelevant - Abnormal, clinically relevant	-	-	-	-	-
Abnormal, clinically relevant - Normal	-	-	-	-	-
Abnormal, clinically relevant - Abnormal, clinically relevant	-	-	-	-	-
Abnormal, clinically relevant - Abnormal, clinically irrelevant	-	-	-	-	-

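### Laboratory shift tables split abnormal values by clinical relevance but not by direction, so new low and new high values share a row

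*SAP*

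**What the plan says.** SAP 5.3.10.4 plans two laboratory summaries. One is a proportion: "the percentage of patients with abnormal clinically relevant values will be assessed". The other is shift-from-baseline tables. The section does not define the shift states and does not mention direction.

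The states appear only in the shells of SAP Appendix 6. In Table 25 the two abnormal categories follow each other as "Abnormal, clinically irrelevant Abnormal, clinically relevant". In Table 27 the list opens with "Normal Abnormal, clinically irrelevant". The shift rows below combine the baseline state with the current state, for example "Normal - Abnormal, clinically relevant". Where one shift row ends and the next begins, the Table 27 shell reads "Abnormal, clinically relevant - - - - - Abnormal, clinically relevant", the dashes being empty cells. Every test in Tables 25-27 has the same nine shift rows, and none carries a low or high label.

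Protocol 8.2.4 promises more: "Laboratory values will be listed with flagging of values outside of normal range, and summarized in shift from baseline tables". Protocol 5.4 secures the reference values: "Normal ranges for the study laboratory parameters must be supplied to Roche before the study starts".

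Protocol 7.3, in its paragraph on diarrhoea and dehydration, shows why direction matters: "There have been rare reports of hypokalaemia and renal failure (including fatalities"). It goes on to ask that renal function and serum electrolytes, potassium among them, be monitored in patients at risk of dehydration.

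**The concern.** A shift table should show how a patient's value moved from baseline. For tests such as potassium, sodium, calcium, glucose or the blood counts, the side of the normal range is part of that answer: a fall and a rise are different safety findings. The planned rows record only whether the investigator thought the abnormality mattered.

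Safety is a secondary objective, and the protocol itself names low potassium as a risk of the study drug. If the shells are filled in as written, a reader of Table 27 who sees patients go from normal to abnormal potassium cannot tell whether they became hypokalaemic or hyperkalaemic. A patient who crosses from one side of the range to the other may be counted as unchanged.

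**Working it through.** No figure in the plan has to be reproduced here. The check counts which directional changes merge in each row, and then looks for another planned output that separates them.

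**Step 1: tests concerned.** SAP 5.3.10.4 and Tables 25-27 cover 4 haematology, 3 coagulation and 13 biochemistry tests: 4 + 3 + 13 = 20. I treat nine as able to be abnormal on either side: hemoglobin, leucocytes, neutrophils and platelets (4), and glucose, calcium, sodium, potassium and chloride (5). The documents do not classify tests this way; the split is an assumption.

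**Step 2: states.** The plan has 3 states, so 3 × 3 = 9 shift rows. Splitting each of the two abnormal states into low and high gives 1 + 2 × 2 = 5 states, and 5 × 5 = 25 directional transitions.

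**Step 3: transitions per planned row.**

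| Planned row (baseline to current) | Rows | Transitions in each | Total |
|---|---|---|---|
| Normal to normal | 1 | 1 × 1 = 1 | 1 |
| Normal to either abnormal state | 2 | 1 × 2 = 2 | 4 |
| Either abnormal state to normal | 2 | 2 × 1 = 2 | 4 |
| Abnormal to abnormal | 4 | 2 × 2 = 4 | 16 |
| Sum | 9 | | 25 |

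Eight of the nine rows therefore pool two or four different changes.

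**Step 4: new abnormalities.** From a normal baseline there are 4 directional outcomes (low or high, irrelevant or relevant). They fall into 2 rows. Within a relevance class, new low and new high always share a row.

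**Step 5: crossings.** From low to high there are 2 × 2 = 4 combinations of relevance. In 2 of them the relevance class is the same at both visits, and the row reads as unchanged. In the other 2 the table shows a change, but only of relevance. Counting high to low as well, 4 of 8 crossings read as unchanged.

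**Step 6: other planned outputs.**

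- *Adverse event tables and Listing 4.* Protocol 7.1.6 sends a treatment-emergent abnormality to the adverse event page, as a diagnosis, if it has symptoms or leads to a change in study drug or concomitant therapy. One that qualifies as a serious adverse event is also recorded there. Direction is then visible. Out-of-range values that do not meet the criteria are to be reported as laboratory abnormalities instead.
- *Laboratory listing.* Protocol 8.2.4 promises it. SAP Appendix 7 has four listings (co-morbidities, ECOG, concomitant medication, adverse events) and none for laboratory values.
- *Toxicity grades.* Both documents say that laboratory variables are graded by NCI CTC-AE 4.0. Tables 25-27 have no grade rows.
- *Means and medians.* SAP 5.3 promises these for continuous variables in general, but the laboratory shells have no rows for them.

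Abnormalities outside the adverse event route thus have no display in the SAP that shows direction.

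**The case against.** The best defence is that the important cases are already visible. Giving treatment for a low potassium would itself be a change in concomitant therapy, so protocol 7.1.6 would make it a named adverse event. This stands, and it limits the gap to abnormalities without symptoms, without any change of treatment and not serious. A reader might infer that the trial's output as a whole cannot tell hypokalaemia from hyperkalaemia. The documents do not support that: the limit applies to the shift tables.

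A reader might also infer that the tables have only one abnormal state, or that every low-to-high change is counted as no change. Neither is right. There are two abnormal states, and half of the low-to-high combinations do show as a change, though not of direction.

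Three further objections have some force:

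- Protocol 7.3 gives a clinical monitoring instruction, not an analysis objective, and calls the reports rare. That is true, and it lowers the weight of the point. It does not make a table without direction informative about a directional risk.
- Scheduled biochemistry is every 8 weeks, so a low potassium during a diarrhoea episode may fall between visits, where no by-visit table shows it. This is a reason to restore the listing as well as to change the tables.
- The row counts describe possible cells, not patients. With about 30 patients, crossings from one extreme to the other may be few. The pooled normal-to-abnormal rows matter more.

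The listing in protocol 8.2.4 would have answered much of the concern, but the SAP does not carry it over.

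**Conclusion.** The point holds as a minor weakness. For nine two-sided tests, Tables 25-27 record the relevance of an abnormality but not its side. New low and new high values in one relevance class cannot be separated there, and a low-to-high change within a class appears as unchanged (2 of 4 combinations). For abnormalities that do not reach the adverse event page, the SAP has no other display that gives direction.

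The conclusion rests on two assumptions: the choice of nine tests as two-sided, and the Appendix 6 shells and Appendix 7 listings being the full planned laboratory output. How many patients would be affected cannot be derived from the documents.

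It would be wrong to read this as a threat to the trial's main result. The display is descriptive, protocol 8.2.2 plans no hypothesis test, and neither ORR nor the sample size depends on it.

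**What to change.** 1. For the nine two-sided tests, define low, normal and high against the local laboratory's normal range and build the shift rows on these states. A 3 × 3 layout needs nine rows, as now. Keep clinical relevance as a separate count within low and within high. Keep the present layout for tests where only one side is of interest, such as AST, ALT, LDH and bilirubin.
2. Add to SAP Appendix 7 the laboratory listing with out-of-range flags that protocol 8.2.4 promises.
3. State the rule in SAP 5.3.10.4, so that the shells are not its only source.

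**Cost.** Splitting the per-visit relevance counts by side replaces three states with five, two more rows per test, or 9 × 2 = 18 rows in all. The 3 × 3 layout gives up the cross-tabulation of relevance over time; keeping it alongside adds nine rows per test. The full five-state cross would need 25 rows per test and is not worth it at about 30 patients. Even the 3 × 3 cells will be sparse.

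Safety tests are run at local laboratories across about 9 centres, so ranges must be mapped per laboratory. Protocol 7.1.6 has results recorded on the eCRF and protocol 5.4 has the ranges supplied before the study starts, so new data collection should not be needed. The sponsor should confirm that numeric results are held, because the SAP tabulates only the three-category judgement.
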